The study design and dosing strategy listed below for Cohorts 3, 4 and 5 are recommendations from the Safety Review Committee following an adhoc safety review meeting held on June 13-14, 2023 to discuss subjects reports of pain and burning at the injection site that were not observed in Part 1 of the study:

• Recommendation: Remove/skip Cohort 3 in Part 2 of the protocol and advance from Cohort 2 to Cohorts 4 and 5. Revert to Part 1 dosing strategy of a 30/70 split dose for all treatments with the injections adminstered 15-minutes apart.

Cohort 3: (N=0): This cohort has been removed at the recommendation of the SRC.

For Part 2 (Cohorts 4 and 5) the highest total daily dose of VP-315 (8.0 mg) will be divided into a split dose; the first dose is not to exceed 2.4 mg (30% of 8-mg dose), and the remaining dose will not exceed 5.6 mg (70% of 8-mg dose) and administered 15 minutes apart (not to exceed 30 minutes).

- Cohort 4 (N= Approximately 30 (10 initial/up to 20 expansion): (Two times weekly dosing) VP-315 once-daily dosing of 8 mg, administered 2 consecutive days in one week (W1D1, W1D2). The planned dosing regimen will be a split dose of VP-315 for all treatments. The 500μL (8 mg) dose will be divided into 2 injections given at least 15 minutes and no more than 30 minutes apart, with 30% (150 μL) administered in the first injection and the remaining 70% (350 μL) with the second injection. Treatment for a second target lesion may begin on D1 of the next week (W2D1, W2D2). Each individual target lesion is treated for the assigned 2 days only (regardless of necrosis status). Up to 2 target lesions may be treated up to 4 total doses.
- Cohort 5 (N= Approximately 30 (10 initial/up to 20 expansion): (Three times weekly dosing) VP-315 once-daily dosing of 8 mg, administered 3 consecutive days in one week (W1D1, W1D2, W1D3). The planned dosing regimen will be a split dose of VP-315 for all treatments. The 500μL (8 mg) dose will be divided into 2 injections given at least 15 minutes and no more than 30 minutes apart, with 30% (150 μL) administered in the first injection and the remaining 70% (350 μL) with the second injection. Treatment for a second target lesion may begin on D1 of the next week (W2D1, W2D2, W2D3). Each individual target lesion is treated for the assigned 3 days only (regardless of necrosis status). Up to 2 target lesions may be treated up to 6 total doses.

See (Table 7-1).

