- Cohort 5 (N= Approximately 30 (10 initial/up to 20 expansion): (Three times weekly dosing) VP-315 once-daily dosing of 8 mg, administered 3 consecutive days in one week (W1D1, W1D2, W1D3. The planned dosing regimen will be a split dose of VP-

315 for all treatments. The  $500\mu L$  (8 mg) dose will be divided into 2 injections given at least 15 minutes and no more than 30 minutes apart, with 30% (150  $\mu L$ ) administered in the first injection and the remaining 70% (350  $\mu L$ ) with the second injection. Treatment for a second target lesion may begin on D1 of the next week (W2D1, W2D2). Each individual target lesion is treated for the assigned 3 days only (regardless of necrosis status). Up to 2 target lesions may be treated – **up to 6 total doses.** 

After receiving a dose, the subject will return to the clinic the following day for assessment by the investigator. If, in the opinion of the Medical Monitor, the lesion is not necrotic Cohorts 1 and 2 only, the same lesion will continue to be treated before any additional target BCC lesions are treated. When a lesion is deemed necrotic in the opinion of the Medical Monitor, the subject will not receive any additional treatment for that lesion.

- If the subject has additional lesions, treatment of the next lesion may begin on D1 of the next week. A maximum of 2 target BCC lesions may be treated, and only 1 lesion may be treated at a time.
- Subjects in Cohorts 4 and 5 with only 1 target lesion that complete week one of treatment and the W1 safety assessment visit without complete necrosis should return for a Limited Safety Assessment Visit on W2D1 for further evaluation of the lesion for necrosis. No additional treatment will be provided.
- Subjects in Part 2 (all Cohorts) that complete week two of treatment and the W2 Safety Assessment Visit without complete necrosis should return for a Limited Safety Assessment visit on W3D1 for further evaluation of the lesion for necrosis. No additional treatment will be provided.

For the first 10 subjects enrolled into Cohorts 4 and 5: after each treatment, subjects will remain in the study center for up to 2 hours post second injection for safety monitoring (e.g., continuous blood pressure, electrocardiographic and AE monitoring).

Following the final treatment of the 10th subject in Cohort 4, enrollment into Cohort 5 may be initiated for 10 subjects.

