**Table 7-1 Dose Regimen (Part 2 Cohorts 1-5)** 

#### CRO must be contacted for each subject before treatment to confirm Cohort assignment

Cohorts	W1D1	W1D2	W1D3	W1D4	W2D1	W2D2	W2D3	W2D4*		
	4 mg loading	8 mg	8 mg	Safety	8 mg	8 mg	8 mg	Safety		
Cohort 1 –										
loading dose (N=3 to 6)	If 1 TRAE SI occurs in the first 3 subjects, enroll up to 6 subjects									
(* * 5 55 5)	— If no further TRAEs SI occur, then begin enrollment into Cohort 2									
	- If	2 TRAEs SI occi	ur in 6 subjects, the	en begin enrollment	into Cohort 3					
	W1D1	W1D2	W1D3	W1D4	W2D1	W2D2	W2D3	W2D4		
Cohort 2 – No	8 mg	8 mg	8 mg	Safety	8 mg	8 mg	8 mg	Safety		
loading dose (N=3 to 6)										
	• If 1 TRAE SI occurs in the first 3 subjects, begin enrollment into Cohort 4 with 30/70 split dosing of 8mg for each treatment									
Cohort 3 – has been removed										

NOTE: Cohorts 1-2: Treatment continues until TRAE (includes TRAE SI) or significant necrosis of Target Lesion #1 as determined by Sub-SRC. If significant necrosis is determined, the current assessment is changed to an assessment-only visit, and no VP-315 is administered for the remaining days of the current Treatment Interval/Week. If the subject has an additional target lesion and a TRAE has not occurred, treatment of Target Lesion #2 may begin at D1W2 of next Treatment Interval/Week. Up to 2 target lesions may be treated. Subjects that complete two weeks of treatment and the W2D4 Safety Assessment Visit without achieving complete necrosis, should return for a Limited Safety Assessment Visit on W3D1 for further evaluation of the lesion for necrosis.

Cohort 4		Lesio	n #1 Treatmei	nt	Lesion #2 Treatment						
2-day dosing regimen	W1D1	W1D2	W1D3	W2D1		W2D1	W2D2	W2D	3	W3D1	
N=30	20/70 9	20/70 9	S a fator	I ''4. J C. C.4.		20/70 9	20/70 9	Safa4		Limited	
(10 initial/ 20 expansion)	30/70 8 mg	30/70 8 mg	Safety Limited Safety		30/70 8 mg	30/70 8 mg	g Safet	y	Safety		
Cohort 5		Lesio	n #1 Treatmer	nt		Lesion #2 Treatment					
3-day dosing regimen	W1D1	W1D2	W1D3	W1D4	W2D1	W2D1	W2D2	W2D3	W2D4	W3D1	
N=30 (10 initial/	30/70 8 mg	30/70 8 mg	30/70 8 mg	Safety	Limited Safety	30/70 8 mg	30/70 8	30/70 8 mg	Safety	Limited Safety	
20 expansion)					Salety		mg			Salety	

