### **3.7. Cohort 5 (N = 37 [10 initial / 27 expansion] at three times weekly dosing)**

Subjects receive VP-315 via once-daily dosing of 8 mg, administered on 3 consecutive days in one week (W1D1, W1D2, W1D3). The planned dosing regimen is a split dose of VP-315 for all treatments. The 500 $\mu$ L (8 mg) dose is to be divided into 2 injections given at least 15 minutes and no more than 30 minutes apart, with 30% (150  $\mu$ L) administered in the first injection and the remaining 70% (350  $\mu$ L) with the second injection. Treatment for a second TL may begin on D1 of the next week (W2D1, W2D2, W2D3). Each individual TL is treated for the assigned 3 days only (regardless of necrosis status). Up to 2 TLs may be treated – up to 6 total doses. Subjects with only 1 TL who complete week one of treatment without complete necrosis receive no additional treatment.

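### In Protocol 7.3.2.2 the Cohort 5 day list for the second lesion stops at W2D2, in conflict with the rest of that bullet and with four other descriptions of the regimen

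*Protocol*

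**What the plan says.** The Cohort 5 bullet in Protocol 7.3.2.2 sets "VP-315 once-daily dosing of 8 mg", "administered 3 consecutive days in one week (W1D1, W1D2, W1D3"), for the first lesion. For the second lesion it says "Treatment for a second target lesion may begin on D1 of the next week (W2D1, W2D2", and there the bracket ends. The Cohort 4 bullet in the same section gives the identical list, W2D1 and W2D2.

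The Cohort 5 bullet then continues: "Each individual target lesion is treated for the assigned 3 days only (regardless of necrosis status"). It closes with a maximum of "up to 6 total doses", and it opens by labelling the cohort as dosed three times a week.

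Four other places describe the second lesion in Cohort 5:

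- Protocol 4.1: "Treatment for a second target lesion may begin on D1 of the next week (W2D1, W2D2, W2D3").
- The Protocol Synopsis lists the same three days.
- Protocol Table 7-1 labels Cohort 5 as a "3-day dosing regimen" and shows a split 8 mg dose for lesion 2 on W2D1, W2D2 and W2D3, with the safety visit on W2D4.
- SAP 3.7: "Treatment for a second TL may begin on D1 of the next week (W2D1, W2D2, W2D3").

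Protocol 7.3 sends the reader to Table 7-1 for the dosing of the Part 2 cohorts.

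**The concern.** The number of dosing days per lesion, two or three, is what separates Cohort 4 from Cohort 5. The primary objective of these cohorts includes information on the dosing regimen for a pivotal study. A day list that gives the second lesion in Cohort 5 the Cohort 4 schedule therefore falls on the variable that the two cohorts exist to describe.

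The line is in the current protocol text, not in the amendment log. Amendment 8 revised other parts of 7.3.2.2 and left it in place.

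The efficacy tables would not reveal a departure. SAP 8 reports efficacy by lesion, SAP 5.5 groups subjects by cohort, and no further subgroups are planned. A Cohort 5 second lesion (TL2) that received two doses would sit unmarked in the Cohort 5 TL2 row. SAP 14, which records where the SAP departs from the protocol, does not mention the discrepancy.

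**Working it through.** The check is a count of doses. It needs no power or sample-size input.

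**Inputs**

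- First-lesion days, Cohort 5: 3 (Protocol 7.3.2.2).
- Second-lesion days, Cohort 5, as printed in 7.3.2.2: 2.
- Second-lesion days, Cohort 5, in the Synopsis, Section 4.1, Table 7-1 and SAP 3.7: 3.
- Days per lesion, Cohort 4: 2 (Protocol 7.3.2.2).
- Daily dose: 8 mg.
- Stated maximum, Cohort 5: 6 doses.

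**Formulas.** Total doses = first-lesion days + second-lesion days. Dose in mg = number of doses × 8.

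**Reproducing the stated maximum**

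- Three-day list: 3 + 3 = 6 doses. This reaches the stated 6. Total 6 × 8 = 48 mg; second lesion 3 × 8 = 24 mg.
- List as printed in 7.3.2.2: 3 + 2 = 5 doses. This does not reach the stated 6. Total 5 × 8 = 40 mg; second lesion 2 × 8 = 16 mg.
- Cohort 4, for comparison: 2 + 2 = 4 doses, total 4 × 8 = 32 mg; second lesion 2 × 8 = 16 mg. Here the stated maximum of 4 is reached exactly.

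**Differences between the two Cohort 5 lists**

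- Second lesion: 1 − 16/24 = 1/3 less.
- Subject total: 1 − 40/48 = 1/6 less.
- On the printed list, the second lesion has the same days and the same 16 mg as in Cohort 4.

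Taken literally, a ceiling of six is not breached by five doses. It is a ceiling that the printed days can never reach. The direct contradiction inside the bullet is with the sentence that assigns three days to each lesion.

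**The case against.** The strongest reply is that the bracket is a lone outlier, probably carried over from the Cohort 4 bullet, and that nobody reading the whole section would dose from it. Much of this stands. The next sentence of the bullet says three days. Table 7-1, which Section 7.3 names as the Part 2 dosing reference, shows a dose on W2D3. Sites must contact the CRO before treatment to confirm the cohort, although that does not itself settle the days. The sub-SRC's real-time review under Protocol 7.4.1 covers dosing instruction. The SAP, written with Cohort 5 at N = 37, still describes three days. These facts make misdosing less likely. They do not remove the contradiction from a dosing instruction.

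A reader might infer more than the documents support, in four ways:

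- **That 7.3.2.2 is the text sites dose from.** No passage says so, and Section 7.3 points to Table 7-1.
- **That TL2 carries no information on two against three days.** That would need every Cohort 5 TL2 to have been dosed on two days. No formal comparison is planned in any case, since the analysis is descriptive.
- **That a site giving two doses would be penalised for following the protocol.** Such a site would also have departed from the next sentence of the bullet. SAP 6 lists only potential major deviations, and SAP 7.2 leaves the classification to the sponsor. Only the secondary per-protocol population is at stake: the full analysis population requires one full dose and a histologic result, so a missing W2D3 dose does not by itself exclude a subject.
- **That TL2 efficacy should be split by doses received.** Protocol 10.2 stops VP-315 after a treatment-related event of special interest. A split into two and three doses would therefore mix stops for toxicity with any dosing that followed the bracket.

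It is also fair to say that the exposure data are already planned. SAP 7.6 summarises expected and actual dose by injection, lesion and visit, including W2D3, and adds a listing with the reasons for doses not given.

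**Conclusion.** The point holds as an internal inconsistency in a dosing instruction. The Cohort 5 second-lesion days in Protocol 7.3.2.2 disagree with the three-day sentence and the six-dose maximum in the same bullet, and with the Synopsis, Section 4.1, Table 7-1 and SAP 3.7.

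For a subject with two treated lesions, the two readings differ by one dose: 5 against 6 doses, 40 mg against 48 mg in total, and 16 mg against 24 mg in the second lesion. These figures assume that every listed dose is given in full at 8 mg. Subjects with one treated lesion are unaffected.

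The consequence is conditional. If a site followed the bracket, that subject's second lesion would have had the Cohort 4 number of days but would be described under Cohort 5. The documents do not show whether this occurred, or how many Cohort 5 subjects had a second lesion treated, so the effect on the TL2 rows cannot be sized from them. The point does not call the TL1 results into question.

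**What to change.** Reconcile the Cohort 5 second-lesion days in Protocol 7.3.2.2 with the rest of that bullet, the Synopsis, Section 4.1, Table 7-1 and SAP 3.7, so that every place states the same days. Which schedule was intended is for the sponsor to confirm.

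For the analysis, use the administration table and listing already specified in SAP 7.6. Count the Cohort 5 subjects with a treated TL2 that lacked a W2D3 dose for a reason other than an adverse event, and report that count with the TL2 results. A W2D3 dose with no record at all should be included, because a site following the bracket might have entered nothing for that day. The termination reasons in SAP 7.1.2 can help to identify stops for toxicity. No new efficacy split and no special rule for classifying deviations is needed.

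The cost is one line of protocol text and one reported count from dosing data already collected.

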The decision to initiate the next higher dose in Part 1 will be made by an SRC (described in Section 7.4) on the basis of a review of all safety data, and laboratory findings.

Subjects will be screened within 42 days prior to receiving the first dose of VP-315 (biopsy may be collected within 90 days of W1D1); procedures are described in Table 8-1. On W1D1, after completion of all predose procedures, study subjects will receive the first dose of VP-315. Thereafter, each subject in Part 1 and Part 2 (Cohorts 1 and 2) will be dosed every day until necrosis of the target lesion for up to 3 consecutive days before entering the notreatment period. Once a target lesion has necrosed, treatment of that lesion stops, and treatment of any subsequent target lesions (up to 2 total) may continue on Day 1 of the following week (see Section 7.3.2).

In Part 1, DLT or visual confirmation of necrosis of all target lesions will result in termination of VP-315 dosing.

In Part 2 (Cohorts 1 and 2) will determine the optimal dosing regimen based on efficacy, safety and tolerability. In Cohorts 4 and 5, the optimal dosing regimen (as determined from Cohorts 1 and 2 or Part 1) will be administered in up to 2 target lesions on either 2 or 3 consecutive days, respectively, regardless of whether necrosis occurs.

Subjects in Part 2 (Cohorts 4 and 5) with only 1 target lesion, that complete week one of treatment and the W1 safety assessment visit without complete necrosis, should return for a Limited Safety Assessment Visit on W2D1 for further evaluation of the lesion for necrosis. No additional treatment will be provided.

Subjects in Part 2 (all Cohorts) that complete week two of treatment and the W2 Safety Assessment Visit without complete necrosis, should return for a Limited Safety Assessment visit on W3D1 for further evaluation of the lesion for necrosis. No additional treatment will be provided.

For the first 10 subjects enrolled into Part 2 (Cohorts 4 and 5): after each treatment, subjects will remain in the study center for up to 2 hours post second injection for safety monitoring (e.g., continuous blood pressure, electrocardiographic and AE monitoring).

Following the final treatment of the 10th subject in Cohort 4, enrollment into Cohort 5 may be initiated for 10 subjects.

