### 7.3 Dosage, Administration, and Schedule

VP-315 will be administered via intradermal injection into a single target lesion (between  $\geq$ 0.5 cm and  $\leq$ 2 cm in longest diameter) using the 1-mL syringe and 30-gauge ½-inch needle provided by Verrica. The subjects should be positioned in a way so that the target lesion lies flat, to avoid any dependent areas that may be susceptible to leakage of VP-315. Subsequent injections for the same lesion will be given in remaining nonnecrotic areas of the lesion, as assessed prior to treatment. In Parts 1 and Part 2 (Cohorts 4 and 5), each 500-μL dose will be divided into 2 injections given at least 15 minutes and no more than 30 minutes apart, with 30% (150 μL) administered in the first injection and the remaining 70% (350 μL) with the second injection. In all parts of the study, the targeted total volume of delivery is 500 μL daily.

In Part 2, refer to Table 7-1 for cohort dosing and regimen.

For all injections, VP-315 is injected intradermally. It is critical to assure adequate and even distribution of VP-315 across the entire base of the lesion. To accomplish this, the first 150 µL is to be injected as centrally as possible such that the VP-315 can distribute radially outward. The second (350-µL) portion shall be injected in a clockface fashion (i.e., 12, 3, 6, 9 o'clock [shown below in Figure 7-1]) as needed to ensure uniform distribution, into the edges of the lesion to infiltrate the entire tumor with VP-315. Insert the needle at a 10- to 20-degree angle for a flat lesion, or at an increased angle for a raised lesion. Subcutaneous injection should be avoided.

9 C 3

Figure 7-1
Injection Pattern for VP-315

The maximum total daily dose of VP-315 in any treatment visit in any subject or cohort must not exceed 8 mg.

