NOTE: Cohorts 4-5: The administration strategy will be based on the recommendation of the SRC, utilizing Part 1 dosing administration of 30/70 split for 2 or 3 consecutive days. Target Lesion #2 may begin at D1 of next Treatment Interval/Week. Each individual target lesion is treated per cohort regimen of 2- or 3-days only (not based on necrosis). Up to 2 target lesions may be treated. Subjects with only 1 target lesion, that complete week one of treatment and the W1 safety assessment visit without complete necrosis should return for a Limited Safety Assessment Visit on W2D1 for further evaluation of the lesion for necrosis. Subjects with 2 target lesions, that complete two weeks of treatment and the W2 Safety Assessment Visit without achieving complete necrosis, should return for a Limited Safety Assessment Visit on W3D1 for further evaluation of the lesion for necrosis.

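### Two necrosis-stop instructions in the protocol carry no cohort limit and, read literally, conflict with the fixed 2- or 3-day dosing of Cohorts 4 and 5 (minor wording error)

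*Protocol*

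**What the plan says.** The fixed regimen for Cohorts 4 and 5 is stated repeatedly:

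- Protocol 4.1: dosing is "on either 2 or 3 consecutive days, respectively, regardless of whether necrosis occurs".
- Protocol 7.3.2.2, Cohort 5: "Each individual target lesion is treated for the assigned 3 days only (regardless of necrosis status". The Cohort 4 bullet says the same for 2 days.
- Note to Table 7-1: "Each individual target lesion is treated per cohort regimen of 2- or 3-days only (not based on necrosis". Section 7.3 makes this table the Part 2 reference: "In Part 2, refer to Table 7-1 for cohort dosing and regimen".
- SAP 3.7: "Each individual TL is treated for the assigned 3 days only (regardless of necrosis status". SAP 3.6 matches for Cohort 4.

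Two places in the protocol read differently:

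- Section 7.3.2.2, in the paragraph after the Cohort 5 bullet: "When a lesion is deemed necrotic in the opinion of the Medical Monitor, the subject will not receive any additional treatment for that lesion". No cohort is named. The sentence before it, on continuing to treat a lesion that is not necrotic, is limited to Cohorts 1 and 2.
- Table 8-1, treatment column header: treatment visits fall on Days 1 to 3 of each week for as long as the lesion has not necrosed. Again no cohort is named.

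**The concern.** Cohorts 4 and 5 share the daily dose and the 30/70 split. They differ in the number of dosing days per lesion. Their primary objective includes learning about the dosing regimen to support a pivotal design, so the 2-day and 3-day exposures should stay distinct.

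A necrosis stop would shorten dosing in the lesions that respond fastest. Dose would then follow from response, and a Cohort 5 lesion stopped after Day 2 would have received the Cohort 4 regimen. Such a lesion could still count under Cohort 5 for efficacy, because the Full Analysis Population in SAP Section 6 needs only one full dose and a histology result. SAP Section 6 also lists dosing errors as potential major deviations, and the conflicting texts leave open whether an early stop for necrosis is one.

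**Working it through.** **1. The stated dose maxima reproduce.** Doses = days per lesion × 2 lesions. Cohort 4: 2 × 2 = 4. Cohort 5: 3 × 2 = 6. Both match Section 4.1, so the stated maxima fit the fixed schedule.

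**2. Does the context limit the stop sentence?** The Cohorts 1 and 2 restriction sits in the preceding sentence and qualifies that one only. The bullets that follow address Cohorts 4 and 5 by name and then all Part 2 cohorts, so the block as a whole is not confined to Cohorts 1 and 2. Elsewhere, in the synopsis and Section 4.1, the protocol limits the necrosis stop expressly to Part 1 and Part 2 Cohorts 1 and 2. The limit is missing here.

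**3. Does Table 8-1 apply to Cohorts 4 and 5?** Yes. Its excision column gives the Part 2 window (Days 84 to 98), and its footnotes c, f, o and t address Cohorts 4 and 5. Sections 4.1 and 7.3.2.2 tell sites to follow it. The necrosis condition in its treatment header therefore reaches these cohorts as written.

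**4. Dose per lesion if the stop rule were followed.** Daily dose 8 mg (Section 4.1). Subjects return the day after each dose for assessment (Section 7.3.2.2), so the earliest stop leaves one dose.

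| Cohort | Planned | Stopped after Day 2 | Stopped after Day 1 |
|---|---|---|---|
| 4 | 2 × 8 = 16 mg | not applicable (complete) | 8 mg; 1 − 8/16 = 50% lost |
| 5 | 3 × 8 = 24 mg | 16 mg; 1 − 16/24 = 33% lost | 8 mg; 1 − 8/24 = 67% lost |

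**5. A separate slip in the same section.** For the second lesion in Cohort 5, Section 7.3.2.2 has "Treatment for a second target lesion may begin on D1 of the next week (W2D1, W2D2", while Section 4.1 has "Treatment for a second target lesion may begin on D1 of the next week (W2D1, W2D2, W2D3". The shorter list would give 3 + 2 = 5 doses, but the same bullet allows up to 6, and Table 7-1 schedules 8 mg on W2D3. This is a typographical omission.

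No alpha, power or sample-size figure is involved: SAP 5.1 and 5.2 plan no sample-size calculation and no formal inference.

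**The case against.** The strongest reply is that no careful reader would be misled. The stop sentence completes a pair whose other half is limited to Cohorts 1 and 2. The bullet just above it says necrosis does not matter for Cohort 5. Section 7.3 names Table 7-1 as the regimen source. The Medical Monitor makes the Part 2 necrosis call centrally, and Table 7-1 requires the CRO to confirm cohort assignment before each subject is treated. All of this stands. It makes the intent recoverable and keeps the point minor. It does not supply the missing limit in either place.

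A reader might infer more than the documents support:

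- *That Table 8-1 gives Cohort 4 a third dosing day.* It does not. The table pools all cohorts, the header is a visit window, and Section 8.2 describes Part 2 weeks as having at most two or three treatment days.
- *That Table 8-1 puts the Cohort 4 safety visit on the wrong day.* Only in part. Its header allows the day after the last injection, which is Day 3 as in Table 7-1, but attaches that alternative to necrosis. A small mismatch remains for lesions that are not necrotic.
- *That footnote p stops dosing.* It asks for a necrosis evaluation before treatment continues. It does not require a non-necrotic result, so it is compatible with fixed dosing.
- *That doses were lost or results distorted.* No document shows a Cohort 4 or 5 dose withheld for necrosis, and no formal comparison of the cohorts is planned.

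**Conclusion.** Minor, but wrong as written. The stop sentence in Section 7.3.2.2 and the necrosis condition in the Table 8-1 treatment header need a cohort limit. Without one they conflict with the regimen set everywhere else for Cohorts 4 and 5.

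The possible effect per lesion is a loss of 33% or 67% of the planned dose in Cohort 5 and 50% in Cohort 4. How many lesions this could touch is unknown, because the documents do not say how many were necrotic before their last planned dose. The per-lesion figures assume full 8 mg doses on each day given and a site that follows the literal stop rule. Stopping for a treatment-related adverse event of special interest (Protocol 10.2) shortens dosing under either reading and is not part of this point.

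**What to change.** In the protocol:

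- Limit the stop sentence in 7.3.2.2 and the necrosis condition in the Table 8-1 treatment header to Part 1 and Part 2 Cohorts 1 and 2, using the scoping already in the synopsis and Section 4.1.
- State in Table 8-1 that Cohort 4 is dosed on Days 1 and 2 and Cohort 5 on Days 1 to 3, whatever the necrosis status, with the safety visit one day after the last injection (Day 3 for Cohort 4).
- Add W2D3 to the Cohort 5 second-lesion days in 7.3.2.2.

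The cost is a few wording edits.

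The SAP (September 2024) gives cohort sizes of 36 and 37 and speaks of expected enrolment in the past tense, so dosing may be complete and the edits may no longer change any dose. In that case, report for Cohorts 4 and 5 how many lesions received all assigned dosing days and how many stopped for necrosis, separately from adverse-event stops. The treatment termination output in SAP 7.1.2 and the administration output in SAP 7.6 already hold what is needed. Necrosis is not among the listed reasons for stopping or for a missed injection, so take it from the necrosis flag in the 7.6 listing, read beside whether each injection was given. No new analysis is required.
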